#### HIV self-testing intervention

SESH implementation team will send out cohort participants an invitation of receiving free HIV testing kit through a confidential message on social media. Our research team had friended the participants on social media (WeChat) which allows private interaction with them. Individuals who would like to receive this test kit will be directed to an online form that allows them to provide an alias (not their real name), an address, and their cell phone number. These three identifiers will be stored separately in Guangzhou in a locked cabinet. Our research assistant will identify the cohort participants by checking whether the mobile phone number is registered in our baseline survey. Men who provide their address will have a test kit mailed to them. The HIV self-testing package will be sent to participants. The HIV self-test kit is organized in partnership with Guangzhou Tongzhi (GZTZ), a local CBO. The test kits will be offered by SESH. The cover of the mail box will be labeled as "gift". The mail boxes will be delivered by a courier service. Individuals will be able to implement and interpret the test wherever they want, but will be encouraged to send a photograph of the test result back to our research team through WeChat, which is convenient with a smartphone and has no cost. Individuals who have questions can also contact the study research office in Guangzhou over phone or through social media. Individuals who have a positive test will be able to contact the study research office for information about linkage to care and counseling.

## 7 Statistical Considerations

#### 7.1 Primary Outcomes

The primary outcome of this study will be HIV test uptake over the previous three months. This will be assessed by self-report during follow up survey and triangulated with HIV testing surveillance data from the CDC. A difference of 10% in testing rate (assuming a proportion of HIV testing of 35% during the crowdsourced intervention period and 25% during the conventional intervention period) was chosen based on existing levels of HIV testing and what would be feasible and have public health importance in the Chinese context. The CDC measurement of the primary outcome will be the difference between HIV testing comparing the three months immediately prior to the intervention and the three months of the intervention.

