## 4.3 Randomization and Stratification

The eight cities will be randomized to initiate intervention in groups of two at three-month intervals (Figure 1). The order of intervention implementation at four cities within each province (Guangdong and Shandong Provinces) will be randomized using SAS software. One city in Guangdong Province and one city in Shandong Province will then begin intervention simultaneously, i.e. city-level randomization will be stratified by province. While waiting to initiate the intervention, cities will continue conventional campaigns that are part of the routine activities of local CDC and CBOs.

Phase	Pre	p.		Inte	erver	ntior	ı									
Months	1	2	3	4	5	6	7	8	9	10	11	12	13	14	15	16
CDC surveillance survey																
Develop intervention and recruit online cohort in 8 cities																
Guangzhou (GD)				*			*			*			*			*
Yantai (SD)				*			*			*			*			*
Jiangmen (GD)				*			*			*			*			*
Jinan (SD)				*			*			*			*			*
Zhuhai (GD)				*			*			*			*			*
Qingdao (SD)				*			*			*			*			*
Shenzhen (GD)				*			*			*			*			*
Jining (SD)				*			*			*			*			*

Figure 1. Stepped-wedge study design

\*represents online survey at baseline and every 3 months thereafter. Gray shading represents roll-out of the intervention. 8 city clusters; 5 time periods; randomization stratified by 2 provinces (Guangdong, Shandong)

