## 5.2.2 CDC Data Collection

MSM surveillance sites in each of the eight cities will have additional questions added about viewing SESH images, social media engagement with SESH, contributing to SESH contests,

exposure to other ongoing campaigns, HIV/syphilis testing, HIV/syphilis test results. All men who enter surveillance sites in these cities will also be invited to take part in the online cohort. Following informed consent, cell phone numbers will be used to link CDC and online survey data sets.

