#### 5.3 Measures

Information on socio-demographics, sexual behaviors, and psychosocial conditions will be collected using standardized online survey tools. Socio-demographic characteristics include participants' age, highest level of education completed, annual income, marital status, sexual orientation, and sexual orientation disclosure. Behavioral and psychosocial variables include self-reported HIV testing, syphilis testing, HIV self-testing, HIV test-associated stigma, frequency of sex, condom use (condomless sex, sex always with condom, and no sex), HIV testing social norms, HIV testing self-efficacy, community engagement, campaign engagement, MSM empowerment.

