### 7.4 Analysis Plan

## 7.4.1 Primary Outcome Analyses

The primary outcome will be self-reported HIV testing uptake in the past three months. We will examine the hypothesis comparing the superiority of the crowdsourced intervention compared to conventional HIV test uptake campaigns. In our study, since the outcome is binary, generalized linear mixed models (GLMM) and generalized estimating equations (GEE) can be used in our study for the primary outcome analysis. However, since we only have eight clusters, GLMM will be used for primary data analysis in our study; GLMM is preferred in studies with a small number of clusters. The model will include intervention status and time as fixed effects and site and individuals as random effects. The estimated intervention effects will be reported with 95% CIs and p values. Descriptive analysis will be

used to summarize the characteristics and behaviours of the participants at baseline and follow-up surveys.

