## 7.4.2 Secondary Outcome Analyses

Similar analyses will be conducted for binary secondary outcomes (continues variables will be categorized into binary variable), including frequency of syphilis testing, frequency of HIV testing (among those with previous HIV testing), condomless sex, community engagement, awareness of HIV status, empowerment and others. In addition, since four cities will implement more intensive in-person events to promote engagement (Guangzhou, Shenzhen, Qingdao, and Jinan) during intervention development, sub-analysis will be conducted to evaluate the potential effect of in-person events to promote HIV testing and other secondary outcomes among Chinese MSM. In addition, secondary analysis will investigate an interaction effect between intervention and community engagement (both for engagement during the intervention development stage and engagement during the intervention implementation stage, at personal level).

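### The CDC version of the primary outcome is a before/after difference with no calendar-time term, so a net trend shared by the cities would show up as intervention effect in the figure meant to support self-report

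*Combined protocol and SAP*

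**What the plan says.** Section 7.1 takes HIV testing in the previous three months, by self-report, as the primary outcome, to be "triangulated with HIV testing surveillance data from the CDC". It then defines the CDC version: "The CDC measurement of the primary outcome will be the difference between HIV testing comparing the three months immediately prior to the intervention", set against the three months in which the intervention runs.

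Section 7.4.1 gives the model: "The model will include intervention status and time as fixed effects and site and individuals as random effects". That section opens by naming self-reported testing as its outcome and does not mention the CDC measure.

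Section 4.3 starts two cities at a time, three months apart, and "city-level randomization will be stratified by province". It adds: "While waiting to initiate the intervention, cities will continue conventional campaigns that are part of the routine activities of local CDC and CBOs". Figure 1 counts eight city clusters and five time periods.

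Section 5.2.2 adds questions at the surveillance sites, among them "exposure to other ongoing campaigns", and links CDC and online records by cell phone number.

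**The concern.** Each city's CDC difference compares two adjacent calendar quarters, so it contains whatever else changed testing between them. A stepped-wedge design randomises the order of starting so that such change can be separated from the intervention. At the four steps 6, 4, 2 and 0 cities are still on conventional campaigns, so the first three steps have concurrent controls. The CDC definition uses none of them.

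What is at stake is the value of the CDC figure as support for the effect estimate. Under rising testing it could appear to confirm an effect that is absent. Under falling testing it could understate a real one. The self-report estimate is adjusted for time and the CDC figure as defined is not, so the two could agree or disagree for reasons unrelated to reporting accuracy.

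**Working it through.** **Inputs.**
- Eight cities, five quarters, two cities (one per province) starting at each of quarters 2 to 5 (4.3, Figure 1).
- Testing 25% under conventional campaigns and 35% under the intervention, a 10-point target (7.1, 7.3).
- Coefficient of variation 0.15 to 0.4 (7.3), so the city SD at 0.4 is 0.4 × 0.25 = 0.10.
- Assumed, because the documents do not give them: the drift, the CDC count per city-quarter, equal counts, and independent samples each quarter.

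**The plan's own figure.** There is none for the CDC measure. For a plausible city-quarter size I borrow the 91 men per city in Table 2, which agrees with the plan's total: 91/(1 − 0.30) = 130, and 8 × 130 = 1040.

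**Bias.** Let b1 to b5 be the shared testing level in each quarter, with no true effect. The mean before/after difference is

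[(b2 − b1) + (b3 − b2) + (b4 − b3) + (b5 − b4)]/4 = (b5 − b1)/4.

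Staggering the starts does not remove a net trend.

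| Assumed shared drift per quarter | True effect | Mean before/after | Period-adjusted |
|---|---|---|---|
| +1 | 0 | +1 (10% of target) | 0 |
| +3 | 0 | +3 (30%) | 0 |
| +5 | 0 | +5 (50%) | 0 |
| −3 | 10 | 7 | 10 |

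Swings that return to their starting level cancel. A seasonal path of 0, 5, 0, −5, 0 gives pair differences +5, −5, −5, +5, mean 0. The period-adjusted estimate is also 0 when drift differs between the provinces, because each step has one city from each.

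**Data used.** The before/after measure uses 8 × 2 = 16 city-quarters. All quarters give 8 × 5 = 40. Control quarters plus the first intervention quarter give 2 × (2 + 3 + 4 + 5) = 28.

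**Precision.** Before/after SE = √(2 × 0.25 × 0.75/(8n)). The adjusted SE comes from generalised least squares with period effects and a random city effect. In points, at coefficient of variation 0.4:

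| n per city-quarter | Before/after | 40 city-quarters | 28 city-quarters |
|---|---|---|---|
| 50 | 3.06 | 3.46 (ratio 1.13) | 3.81 (1.25) |
| 91 | 2.27 | 2.59 (1.14) | 2.87 (1.26) |
| 200 | 1.53 | 1.76 (1.15) | 1.96 (1.28) |

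At 0.15 the ratios are 1.04, 1.08 and 1.11 (40) and 1.13, 1.17 and 1.22 (28).

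In the 28 version both cities observed in quarter 5 are exposed, so the period effect absorbs them and they carry no weight. The SE is 2.87 with or without those two city-quarters.

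**Break-even.** Under steady shared drift d, the before/after mean squared error is SE² + d². Adjustment lowers root mean squared error when d exceeds √(adjusted SE² − before/after SE²). At n = 91 and 0.4:
- 40 city-quarters: √(2.587² − 2.270²) = 1.24, about 1.2 points per quarter.
- 28 city-quarters: √(2.871² − 2.270²) = 1.76, about 1.8 points per quarter.

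**Only each city's own two quarters.** With city and period fixed effects the design matrix has rank 12 of 13, so the effect is not identified. With a random city effect it is estimable, but the SE at n = 91 and 0.4 is 4.12, against 2.27.

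**The case against.** The strongest reply is that 7.1 defines a measurement, not a model. Nothing says that the CDC difference will be tested or that adjustment for time is ruled out. That is true, and a reader should not infer that the plan forbids adjustment. But the definition does fix the comparison as two adjacent quarters, and no other section gives the CDC measure a different analysis.

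Triangulation is also undefined. With records linked by phone number, it may mean checking a man's self-report against his CDC record. A shared trend does not affect that use, so the point is confined to the CDC difference read as an effect estimate.

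No trend is documented. The survey item on other campaigns shows that outside influences were anticipated, not that testing was drifting. The 5-point case implies a 20-point rise over four quarters from a 25% base and is an upper illustration. At 1 point per quarter, with 91 men and a coefficient of variation of 0.4, adjustment has the larger root mean squared error. All of this stands and limits the size of the point.

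Finally, the shading of Figure 1 is not shown in the text available, so I cannot tell which CDC quarters exist. The fix has to be conditional on that.

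Two stronger readings are tempting. One is that the trial's primary result is biased; 7.4.1 adjusts the self-report outcome for time, so it is not affected by this. The other is that seasonality alone would distort the CDC figure; a swing that returns to its starting level cancels in the eight-city mean.

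**Conclusion.** The point holds for the CDC effect figure only. As defined, it passes a shared net trend straight into the estimate, at one quarter of the change from the first to the fifth quarter: 1, 3 or 5 points for assumed drifts of 1, 3 or 5 points per quarter. The direction and size of any real drift are unknown.

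The result assumes an equally weighted mean over eight cities and drift common to the cities (or to the cities within each province). City-specific drift is not removed by the period-adjusted model. This is a worthwhile and inexpensive improvement to a supporting check, not a fault in the primary analysis.

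**What to change.** In 7.1 and 7.4.1:

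1. State which CDC quarters will be obtained for each city, and whether triangulation means comparing effect estimates, checking linked individual records, or both.
2. Where data exist by city and calendar quarter, analyse them with intervention status and period as fixed effects and city as a random effect.
3. State the estimand. Using 28 city-quarters keeps the first intervention quarter, as 7.1 has it, but the last pair's quarter-5 data then carry no weight. Using 40 changes the target to all exposed quarters.
4. Report the simple before/after difference beside the adjusted estimate, labelled descriptive. If only each city's own two quarters exist, report it as descriptive only and do not use it to corroborate the effect estimate.
5. State that the model removes drift common to the cities but not city-specific drift.

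**Cost.** SAP wording and one further model; Section 9 says that outcomes and analysis are still pending. It may also need more CDC data, 28 or 40 city-quarters in place of 16. Over 50 to 200 men per city-quarter and a coefficient of variation of 0.15 to 0.4, the SE rises by 4% to 15% (40) or 13% to 28% (28).

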## 7.2 Secondary Outcomes

A number of secondary outcomes will also be measured. These include syphilis testing, condomless sex, community engagement, testing stigma, and others (Appendix 1). Outcomes will also be stratified based on the level of engagement in developing the intervention, and based on the personal level of engagement during the stage of intervention implementation.

## 7.3 Sample Size Calculation

We used a binary outcome stepped-wedge randomized controlled trial design for sample size calculation. The required sample size is calculated for the primary outcome. To calculate sample size, we assumed that a crowdsourced intervention will be superior to a conventional method in promoting HIV testing among MSM who never tested for HIV. Assuming a proportion of HIV testing of 35% during the crowdsourced period and 25% during the conventional period, total number of clusters of eight, total number of time period for intervention of four, coefficient of variation of 0.4 (usually between 0.15 and 0.4), 2-sided alpha=0.05, 90% power, and 30% loss to follow up, then the total sample size will be 1040 men (130 for each city). To further improve the power for sub-analysis and secondary outcomes, we will increase the sample size to 1280 men (160 for each city). The calculation was made using the formulas developed by Michael A. Hussey et al. (http://faculty.washington.edu/jphughes/pubs.html).

Table 2	: samp	le size	calculation
---------	--------	---------	-------------

		NT I						Loss	Sample	Total
		Number	Number	Coefficient			Sample	to	size for	sample
Pi*	Pc \$	of	of time	of	Alpha	Power	size/no	follow	aach	size (8
		clusters	periods	variation @			LTFU	10110 W	cacii	5120 (0
			-					up	cluster	clusters)

30	20	8	5	0.4	0.05	0.9	80	30%	114	912
30	20	8	5	0.15	0.05	0.9	71	30%	101	808
30	15	8	5	0.4	0.05	0.9	31	30%	44	352
30	15	8	5	0.15	0.05	0.9	26	30%	37	296
35	25	8	5	0.4	0.05	0.9	91	30%	130	1040
35	25	8	5	0.15	0.05	0.9	83	30%	119	952
35	20	8	5	0.4	0.05	0.9	37	30%	53	424
35	20	8	5	0.15	0.05	0.9	31	30%	44	352
40	30	8	5	0.4	0.05	0.9	99	30%	141	1128
40	30	8	5	0.15	0.05	0.9	93	30%	133	1064
40	25	8	5	0.4	0.05	0.9	42	30%	60	480
40	25	8	5	0.15	0.05	0.9	36	30%	51	408
45	35	8	5	0.4	0.05	0.9	104	30%	149	1192
45	35	8	5	0.15	0.05	0.9	99	30%	141	1128
45	30	8	5	0.4	0.05	0.9	45	30%	64	512
45	30	8	5	0.15	0.05	0.9	40	30%	57	456

Note: \*Pi: probability of HIV testing during intervention period; \$Pc: probability of HIV testing during control period; @ usually between 0.15-0.4.

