## 5 Trial Population and Measures

## 5.1 Eligibility

Eligibility criteria will include: currently living and planning to live in the eight cities for the next 12 months; not living with HIV; no HIV test in the past three months; born biologically male and identify as either male or transgender; had oral or anal sex with men at least once during their lifetime; 16 years and older; willing to provide cell phone number (for follow up and incentive delivery purposes); completed the informed consent document. MSM who meet all other eligibility criteria but received testing in the past three months or living with HIV will be invited to complete a single survey, but not followed over time in the cohort.

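### Table 2 counts the baseline survey as an outcome period, but eligibility fixes the primary outcome at zero there, so the 90% power at 1040 men rests on five periods when only four carry data

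*Combined protocol and SAP*

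**What the plan says.** - **Sample size (7.3).** For testing rates of 35% against 25%, eight clusters and a coefficient of variation (CV) of 0.4, the plan states "2-sided alpha=0.05, 90% power, and 30% loss to follow up, then the total sample size will be 1040 men (130 for each city"). The Table 2 row behind this has five periods and 91 men per city before loss. The text of 7.3 instead gives "total number of time period for intervention of four".
- **Design (4.3, Figure 1).** The legend reads "8 city clusters; 5 time periods; randomization stratified by 2 provinces (Guangdong, Shandong"). Surveys are marked at months 4, 7, 10, 13 and 16, which is a baseline and four follow-ups.
- **Eligibility (5.1).** The cohort requires "no HIV test in the past three months". Men who otherwise qualify but "received testing in the past three months or living with HIV will be invited to complete a single survey, but not followed over time".
- **Outcome (7.1, 7.4.1).** "The primary outcome of this study will be HIV test uptake over the previous three months", by self-report at follow-up. The mixed model has intervention and time as fixed effects, and site and individual as random effects. The section does not say whether the baseline wave enters.
- **Population sized (7.3).** "we assumed that a crowdsourced intervention will be superior to a conventional method in promoting HIV testing among MSM who never tested for HIV".
- **Margin (7.3).** "To further improve the power for sub-analysis and secondary outcomes, we will increase the sample size to 1280 men (160 for each city").

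**The concern.** The entry criterion and the primary outcome cover the same three months. A man who tested in that window is kept out of the cohort, so no cohort man can have the event at baseline in any city. The stepped-wedge formula assumes that this wave is a control period with a 25% rate and ordinary variation between cities. It has neither, and it tells us nothing about the effect.

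Two things are at stake. One is the stated 90% power at 1040, and with it the claim that the increase to 1280 is spare capacity for other analyses. The other is the model. If baseline enters with a separate effect for each wave, that wave has no events and its log-odds has no finite estimate. If time is fitted more smoothly, a block of guaranteed zeros counts as control data and could favour the intervention.

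A smaller point is that 7.3 sizes the trial for men who have never tested. Section 5.1 does not require this, and 7.4.2 plans an outcome restricted to previously tested men.

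**Working it through.** **Inputs.** From 7.3 and Table 2: rates 0.35 and 0.25 (difference 0.10, mean 0.30), 8 cities, CV 0.4, two-sided 0.05, 90% power, 30% loss. From 4.3: two cities cross at each of four steps. The figure's shading is not visible, so I assume 0, 2, 4, 6 and 8 treated cities at months 4, 7, 10, 13 and 16.

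**Formula (Hussey and Hughes, as cited in 7.3).** With I cities, T periods and N men per city per period:

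Var = I·s²(s² + Tτ²) / [(IU − W)s² + (U² + ITU − TW − IV)τ²]

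- s² = 0.30 × 0.70 / N = 0.21/N.
- τ = 0.4 × 0.30 = 0.12, so τ² = 0.0144.
- U = 2 + 4 + 6 + 8 = 20.
- W = 4 + 16 + 36 + 64 = 120.
- V = 2 × (16 + 9 + 4 + 1) = 60.
- Power = Φ(0.10/SE − c), with c = 1.960 (normal) or 2.365 (t on 7 df).

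**The plan's own figure.** The loss step is right: 91/0.7 = 130, and 130 × 8 = 1040. The 91 depends on c. With five periods, the normal quantile needs 72 per city and matches no row of Table 2 at 90% power. The t value needs 91.2, or 92 rounded up. Across the 16 rows, rounded up, the t value matches 9 exactly and all within 2 men (mean absolute error 0.8%).

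**Five periods, N = 91.** s² = 0.002308.
- Numerator: 8 × 0.002308 × (0.002308 + 0.0720) = 0.001372.
- Denominator: 40 × 0.002308 + 120 × 0.0144 = 1.8203.
- SE = 0.02745 and 0.10/SE = 3.643.

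**Four follow-up periods, N = 91.** U, W and V are unchanged, because baseline had no treated city. The τ² multiplier falls from 120 to 400 + 640 − 480 − 480 = 80.
- Numerator: 8 × 0.002308 × (0.002308 + 0.0576) = 0.001106.
- Denominator: 0.0923 + 1.152 = 1.2443.
- SE = 0.02981 and 0.10/SE = 3.354.

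**Four periods, N = 112** (160 × 0.7, the 1280 plan). s² = 0.001875, SE = 0.02696 and 0.10/SE = 3.709.

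| Case | Power, normal | Power, t (7 df) |
|---|---|---|
| Five periods, 91 per city (1040) | 95.4% | 89.9% |
| Four periods, 91 per city (1040) | 91.8% | 83.9% |
| Four periods, 112 per city (1280) | 96.0% | 91.1% |

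**Numbers needed for 90% power with four periods.**

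| | Normal | t (7 df) | Stated |
|---|---|---|---|
| Per city before loss | 85 | 109 | 91 |
| Per city after 30% loss | 122 | 156 | 130 |
| Total | 976 | 1248 | 1040 |
| Left from 1280 | 304 | 32 | 240 |

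Within each convention, losing baseline raises the requirement by about 18% (72 to 85, or 92 to 109). For the 35/25 row at CV 0.15, four periods need 70 (normal) or 92 (t) per city, against 83 printed. Under t, the eight CV 0.4 rows rise 17% to 21% above print and the eight CV 0.15 rows rise 0% to 15%.

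**The case against.** **The power loss depends on an unstated convention.** With a normal quantile, 1040 men still exceed 90% on four periods. The t value was found by searching for a match to Table 2. A normal quantile at about 95% power, with τ = CV × the intervention rate, also comes within 2 men on every row (5 exact, mean error 1.6%). That contradicts the table's printed 90%, so t remains the better reading, but it is inferred. This objection stands, which is why both results are shown.

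**The t figures pair a t critical value with a normal tail.** A noncentral t on 7 df gives 81.9% at 1040 and 88.7% at 1280 with four periods. It gives 87.6% for the printed row, so it is not how Table 2 was made. It does mean that the assurance of at least 90% at 1280 holds only for the formula used above.

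**Follow-up-only outcome data may already be intended.** Section 7.1 refers to follow-up surveys, and the four periods in the text of 7.3 can be read as four steps after a baseline. That makes the addition to 7.4.1 a clarification. It does not help Table 2, which counts five.

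**Screening might precede the month-4 survey.** Figure 1 has a separate recruitment row, so some men could test between screening and baseline. The single-survey wording in 5.1 points to one instrument. The restriction would cease to matter only if the gap were a full three months.

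**CDC surveillance data could supply pre-intervention testing.** Section 7.4.1 makes self-report the primary outcome, so these data do not fill the baseline wave.

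**Conclusion.** The concern holds. Table 2 credits a wave in which the primary outcome is zero by eligibility, and this understates the required number by about 18% in the row that the trial relies on. At 1040 men, power is about 84% under the convention that best fits Table 2 and about 92% under a normal quantile, so a shortfall below 90% is likely but not proven. Planned enrolment of 1280 gives about 91% or 96% on the same formula, and the trial should not be called underpowered on this ground. What shrinks under the t value is the margin for sub-analyses and secondary outcomes, from 240 men to 32. Under the normal quantile it is 304.

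These figures keep the plan's rates and CV of 0.4, use the mean rate for the variance, assume the roll-out above, and treat the waves as separate samples, as the cited formula does. The individual random effect in 7.4.1 is not in the calculation. The never-tested wording and the missing critical value are lesser points that should be corrected at the same time.

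**What to change.** 1. **Section 7.3 and Table 2.** State the critical value (normal, or t with its degrees of freedom) and the variance convention. Set the outcome periods to four (months 7, 10, 13 and 16), recompute all 16 rows, and restate power at 1040 and at 1280. Make the period count in the text agree with the table.
2. **Section 7.3, population.** Replace the reference to never-tested men with the cohort that section 5.1 enrols: MSM not living with HIV and untested in the three months before entry.
3. **Section 7.4.1.** Add a sentence such as: *The baseline wave is not an outcome period in the GLMM; the outcome waves are the four follow-up surveys.*

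The cost is one rerun of the formula and a few changed lines, and enrolment stays at 1280. If the t value was used, the plan will have to state lower power at 1040 (about 84%) and acknowledge that little of the 1280 remains for sub-analyses and secondary outcomes.
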